 - Platelet count $\geq 100 \times 10^9/L$.
 - Hemoglobin ≥ 9.0 g/dL. No transfusions are allowed within 2 weeks (14 days) prior to enrollment.
 - Creatinine clearance ≥ 45 mL/min (refer to [Attachment 7](#) for the Cockcroft-Gault formula).
 - Proteinuria ≤ 1000 mg in 24 hours (if routine urinalysis indicates $\geq 2+$ proteinuria).
 - Total bilirubin below upper limit of normal (ULN) (except for patients with Gilbert's Syndrome, who must have a total bilirubin < 3 mg/dL).
 - Alanine aminotransferase (ALT)/aspartate aminotransferase (AST) $\leq 3.0 \times$ ULN; if the liver has tumor involvement, AST and ALT $\leq 5.0 \times$ ULN are acceptable.
 - An adequate coagulation function as defined by International Normalized Ratio $\leq 1.5 \times$ ULN or prothrombin time $\leq 1.5 \times$ ULN, and partial thromboplastin time or activated partial thromboplastin time $\leq 1.5 \times$ ULN if not receiving anticoagulation therapy. For patients receiving anticoagulants, exceptions to these coagulation parameters are allowed if they are within the intended or expected range for their therapeutic use. Patients must have no history of active bleeding (defined as within 14 days of first dose of study drug) or pathological condition that carries a high risk of bleeding (for example, tumor involving major vessels or known esophageal varices).
- [10] Have left ventricular ejection fraction (LVEF) $\geq 50\%$ assessed within 28 days prior to enrollment.
- [11] Females of child-bearing potential must have a negative serum or urine pregnancy test within 7 days prior to enrollment.

- Exceptions: females not of child-bearing potential due to surgical sterilization (at least 6 weeks following surgical bilateral oophorectomy with or without hysterectomy or tubal ligation) confirmed by medical history or menopause.

A “postmenopausal woman” is a woman meeting either of the following criteria:

- spontaneous amenorrhea for at least 12 months, not induced by a medical condition such as anorexia nervosa and not taking medications during the amenorrhea that induced the amenorrhea (for example, oral contraceptives, hormones, gonadotropin releasing hormone, antiestrogens, selective estrogen receptor modulators, or chemotherapy)
- spontaneous amenorrhea for 6 to 12 months and a follicle-stimulating hormone level >40 mIU/mL

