7.2.3. Dose Modifications

7.2.3.1. Dose Delays, Modifications, and Discontinuations

After treatment has been initiated, in order to start the next cycle, the following criteria must be fulfilled:

- ANC $\geq 1.0 \times 10^3/\mu\text{L}$ (1000/ μL ; $\geq 1.0 \times 10^9/\text{L}$)

Note that in order to administer single-agent olaratumab on Day 8, ANC must be $\geq 750/\mu\text{L}$; $\geq 0.75 \times 10^9/\text{L}$. If the ANC is $< 750/\mu\text{L}$, the Day 8 administration of olaratumab may be delayed for a maximum of 7 days. If the ANC level has not increased to $\geq 750/\mu\text{L}$ within 7 days, then the Day 8 olaratumab dose in that cycle should be skipped and dosing resumed on Day 1 of the following cycle if criteria for dosing are met. If all dosing criteria are met, a delay or omission of the Day 8 olaratumab dose should not result in a delay of the Day 1 olaratumab dose of the following cycle.

- Platelets $\geq 100 \times 10^3/\mu\text{L}$ (100,000/ μL ; $\geq 100 \times 10^9/\text{L}$)
- Hemoglobin ≥ 8 g/dL
- Creatinine clearance ≥ 45 mL/min (refer to [Attachment 7](#) for the Cockcroft-Gault formula)
- Proteinuria ≤ 1000 mg in 24 hours (if routine urinalysis indicates $\geq 2+$ proteinuria) (to be performed every other cycle)

- Total bilirubin below ULN
- AST and ALT $\leq 3.0 \times$ ULN, or $\leq 5 \times$ ULN if the transaminase elevation is due to liver metastases
- Olaratumab-related AEs that are NCI-CTCAE Version 4.0 Grade <2 or equivalent severity to baseline

Delays:

In general, dose delays of 1 study drug (olaratumab or doxorubicin) due to toxicity guidances outlined in Sections 7.2.3.1.1 and 7.2.3.1.2 will not necessitate delays of the other study drug.

Treatment may be delayed for up to 21 days (1 equivalent cycle) to allow a patient sufficient time for recovery from study drug-related toxicity. If a patient does not recover from the toxicity within 42 days (2 equivalent cycles) from Day 1 of the previous treatment cycle, then the patient must be discontinued from study therapy.

Any procedure or sample collection whose timing is related to olaratumab dosing is to be completed according to when the olaratumab dose was actually administered, not when that dose was expected to occur. Samples whose adjusted timing would fall outside of the treatment cycle duration due to dose delay may be omitted.

Dose Modifications:

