	6.1	Vital Signs	X	X	X	X	Vital signs include blood pressure, pulse, and temperature. During the Observation Period (initial 2 cycles of olaratumab therapy), collect vital signs 3 times: 
 • within 15 minutes (+5 minutes) prior to olaratumab infusion • within 1 hour (+5 minutes) after completion of the olaratumab infusion • within 1 hour (+5 minutes) after completion of the doxorubicin infusion. Thereafter (Cycles 3+), obtain vital signs 2 times: within 15 minutes (+5 minutes) prior to olaratumab infusion within 1 hour (+5 minutes) after completion of the doxorubicin infusion.		
Lab/ Diagnostic Tests	Attachment 2	Hematology	X	X	X	X	Laboratory assessments may be done within 7 days prior to D1 and D8 of each cycle. See Attachment 2 for details. Testing will be performed locally for patient management and centrally for analysis purposes.		
	Attachment 2	Serum Chemistry	X		X		Laboratory assessments may be done within 7 days prior to D1 of each cycle. See Attachment 2 for details. Testing will be performed locally for patient management and centrally for analysis purposes.		
	Attachment 2	Coagulation Profile	X		X		Perform on D1 every other cycle or as clinically indicated. See Attachment 2 for details. Testing will be performed locally only.		
	Attachment 2	Urinalysis	X		X		Laboratory assessments may be done within 7 days prior to D1 of every other cycle or as clinically indicated. Includes a routine UA, and, if clinically indicated, a microscopic analysis. If routine analysis indicates >2+ proteinuria, then a 24-hour urine must be collected and must demonstrate ≤1000 mg of protein in 24 hours. Testing will be performed locally only.		
	Attachment 2	Pregnancy Test	X		X		Serum β-HCG or urine pregnancy test on D1 of every cycle or per local practice (whichever is of shorter duration). If a pregnancy test performed on D1 of the cycle is positive, confirm with a serum or urine pregnancy test (pregnancy test results are not recorded on the eCRF). If results are positive, the investigator is to consult with the Lilly CRP. Testing will be performed locally only.		
	8.2.2 Attachment 4	PK Samples	See Attachment 4 for specific time points					Whole blood samples collected for olaratumab serum PK measurements.	

Procedure Category	Protocol Section	Procedure	Study Period				Treatment Period				Comments

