			Olaratumab Monotherapy		Combination Therapy Olaratumab + Doxorubicin		Olaratumab Monotherapy		Combination Therapy Olaratumab + Doxorubicin		
			1		2-7		1		2-7		
			1 ^{a,b}	8 ^a	1 ^{a,b}	8 ^a	1 ^{a,b}	8 ^a	1 ^{a,b}	8 ^a	
	8.2.5 Attachment 4	Immunogenicity Samples	See Attachment 4 for specific time points				Whole blood samples collected. If a patient experiences an IRR to olaratumab, blood samples for immunogenicity and PK analysis will be taken at the following time points: (1) as soon as possible after the onset of the IRR, (2) at the resolution of the IRR, and (3) 30 (± 3 days) days after onset of the IRR event.				
Lab/ Diagnostic Tests	8.2.4	Pharmacogenetic Whole Blood Sample for DNA storage	X							Whole blood sample collected. It is highly recommended to draw the whole blood sample prior to the first dose (C1D1 at predose); however, it can be collected later during the study if necessary.	
	8.2.3 Attachment 4	Plasma sample for exploratory biomarkers	X		See Attachment 4 for specific time points					Plasma sample collected. C1D1 at predose, C2D1 (combination therapy pre-dose) and at the end of the patient's study treatment. See Section 8.2.3.1 and Attachment 4 for details and specific time points.	
	8.2.3 Attachment 4	Serum sample for exploratory biomarkers	X		See Attachment 4 for specific time points					Serum sample collected. C1D1 at predose, C2D1 (combination therapy pre-dose) and at the end of the patient's study treatment. See Section 8.2.3.1 and Attachment 4 for details and specific time points.	
	8.2.3 Attachment 4	Mandatory Whole Blood Collection for Circulating Tumor Cells	X		See Attachment 4 for specific time points					Collect mandatory peripheral whole blood samples predose at C1D1, C1D8, C2D1, C2D8, and C3D1, and at end of the patient's study treatment or at the time of surgical resection. See Section 8.2.3.1 and Attachment 4 for details.	
	8.2.3	Mandatory Tumor Tissue				X				Mandatory tumor tissue must be collected up to 3 days prior to the first dose of C2D1. When submitting a specimen from a tumor resection after or during combination therapy, sites should examine samples to determine adequacy of tumor tissue using their local laboratory procedures. If additional tumor biopsies are collected as part of clinical care, they should be submitted, along with pathology reports, for further analysis. See Section 8.2.3.2 for details.	

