Attachment 2. Protocol JGDM Clinical Laboratory Tests

All laboratory screening evaluations are to be performed within 14 days prior to enrollment, unless otherwise specified. Eligibility for inclusion in this clinical trial will be based on local clinical laboratory results (not transcribed onto electronic case report forms); duplicate samples will be submitted to the central laboratory. Treatment decisions may be based upon results of tests performed locally. Discrepancies between local and central laboratory that may have an impact on eligibility or treatment decisions will not be considered protocol deviations. On-study clinical laboratory tests assayed for patient safety (such as hematology, serum chemistry, coagulation, and pregnancy tests) are to be collected prior to study treatment.

Clinical Laboratory Tests**Hematology^{a,b}**

Hemoglobin
 Hematocrit
 Erythrocyte count (RBC)
 Mean cell volume
 Mean cell hemoglobin concentration
 Leukocytes (WBC)
 Neutrophils
 Lymphocytes
 Monocytes
 Eosinophils
 Basophils
 Platelets

Coagulation Test^a

Prothrombin time (PT)
 Partial Thromboplastin Time (PTT)
 International normalized ratio (INR)

Urinalysis^{a,c}

Specific gravity
 pH
 Protein
 Glucose
 Ketones
 Blood

Urine leukocyte esterase

Other^d

Immunogenicity samples
 PK samples
 Biomarker samples

Clinical Chemistry^{a,b}**Serum Concentrations of the following:**

Sodium
 Potassium
 Total bilirubin
 Alkaline phosphatase
 Alanine aminotransferase (ALT)
 Aspartate aminotransferase (AST)
 Blood urea nitrogen (BUN)
 Creatinine
 Uric acid
 Calcium
 Glucose, random
 Albumin
 Total protein
 Chloride
 Thyroid-stimulating hormone
 Direct bilirubin

Pregnancy test^{a,c}**Follicle-stimulating hormone (FSH)^{a,f}**

Abbreviations: CRP = clinical research physician; D = Day; PK = pharmacokinetics; RBC = red blood cells; WBC = white blood cells

- a Assayed by local or investigator-designated laboratory.
- b Duplicate samples will also be assayed by a sponsor-designated laboratory.
- c If urinary protein is $\geq 2+$ at evaluations, a 24-hour urine collection (to assess protein) must be collected and must be ≤ 1000 mg of protein in 24 hours (up to 3 business days is allowed if the weekend).
- d Assayed by a sponsor-designated (central) laboratory.

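### Gilbert's syndrome patients may enter with total bilirubin up to 3 mg/dL, but the rule for starting Cycle 2 requires bilirubin below ULN with no matching exception

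*Protocol*

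**What the plan says.** Protocol Section 6.1.1, criterion 9, requires total bilirubin below ULN within 14 days before enrollment. It makes one exception, for patients with Gilbert's "Syndrome, who must have a total bilirubin" under 3 mg/dL.

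Protocol Section 7.2.3.1 governs treatment once it has begun: "in order to start the next cycle, the following criteria must be fulfilled". The bilirubin item in that list reads "Total bilirubin below ULN", without qualification. Two other items do carry qualifications. Transaminases have a higher limit when the elevation comes from liver metastases, and olaratumab-related adverse events may be at a severity equivalent to baseline.

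The same section allows a delay of up to 21 days "to allow a patient sufficient time for recovery from study drug-related toxicity".

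The doxorubicin hepatic section (7.2.3.1.2.3) gives a contraindication above 5.0 mg/dL or in Child-Pugh Class C, and otherwise refers back to Section 7.2.3.1. The SAP does not mention Gilbert's syndrome.

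**The concern.** The same bilirubin value can satisfy the protocol at entry and fail it three weeks later, although nothing about the patient has changed. The patient would by then have had a mandatory pre-treatment biopsy and a cycle of single-agent olaratumab. The planned combination would be barred by a value already known at screening. The site would have to withhold the combination or give it in breach of a mandatory criterion. In the second case the dosing could be listed as an important deviation under SAP Section 5.6. Protocol Section 5.4 describes early tumor reduction as an important aim in this potentially resectable population, so the bar matters to the patient concerned.

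**Working it through.** The plan gives no figure to reproduce, and no sample size, power or event count enters. The check sets the two limits side by side and then looks for any provision that reconciles them.

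**The two limits.** Let B be a Gilbert's patient's stable total bilirubin.

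| B | Entry (criterion 9) | Start of next cycle (7.2.3.1) |
|---|---|---|
| B < ULN | passes | passes |
| ULN ≤ B < 3 mg/dL | passes, through the exception | fails |
| B ≥ 3 mg/dL | fails | fails |

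The middle row is the conflict. The documents give no ULN value. For any ULN below 3 mg/dL the interval from ULN to 3 mg/dL is not empty, and the entry exception would relax nothing if ULN were 3 mg/dL or more. A Gilbert's patient below ULN meets the general limit anyway. The patients who actually need the entry exception are therefore the ones who fail the cycle-start rule if their value is unchanged.

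**When it applies.** The list covers the next cycle after treatment has begun, so Cycle 1 is not blocked. The first check is at Cycle 2 Day 1, when combination therapy begins. Attachment 1 supplies the value: "Laboratory assessments may be done within 7 days prior to D1 of each cycle". The item applies to the start of the cycle as a whole, olaratumab included.

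**Possible ways out in the current text.**

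- The baseline allowance in Section 7.2.3.1 is attached to olaratumab-related adverse events, not to the bilirubin item.
- The 21-day delay and the 42-day discontinuation limit are written for recovery from toxicity. A constitutional value is not toxicity, and waiting is not expected to lower it.
- The provision that a delay of one drug need not delay the other refers to the drug-specific toxicity guidance in Sections 7.2.3.1.1 and 7.2.3.1.2, not to this list.
- Section 7.2.3.1.2.3 adds a contraindication above 5.0 mg/dL and no exception below it.
- Section 6.3.2 lets the investigator end treatment. It does not let a cycle start.
- Attachment 2 excuses discrepancies between local and central laboratories. That does not help when the value itself is at or above ULN.

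None of these reconciles the two limits.

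**The case against.** The strongest reply is that this is a small wording mismatch. It needs a Gilbert's patient, among about 35 enrolled, whose bilirubin is at or above ULN at a cycle-start check. The documents give no frequency, and the number may be zero. Patients who are nonevaluable for the primary objective may be replaced (Sections 7.6.1 and 10.1.1). This limits the weight of the point but does not make the two rules agree.

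A second reply is that the documents do not show which limit is wrong. This stands. The entry list has two hepatic exceptions, and the cycle-start list keeps only the one for transaminases, which suggests an oversight without proving it. Sections 7.2.3.1.2.1 to 7.2.3.1.2.4 give no bilirubin-based doxorubicin reduction between ULN and 5.0 mg/dL, and Section 7.1.3 sends investigators to the package insert for dose modifications. Simply relaxing the rule would allow 75 mg/m² at bilirubin approaching 3 mg/dL with no dose guidance in the protocol. The clinical question has to be settled first.

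A reader might also infer more than the documents support:

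- **That primary biomarker samples are lost.** Attachment 1 says "Mandatory tumor tissue must be collected up to 3 days prior to the first dose of C2D1", and Section 7.2.3.1 adds "Samples whose adjusted timing would fall outside of the treatment cycle duration due to dose delay may be omitted". However, the second biopsy is mandatory after the lead-in cycle and before combination therapy (Sections 6.2 and 8.2.3.2), so it does not depend on passing the bilirubin check. Uncertainty about timing around a delayed Cycle 2 arises with any delay and is not specific to Gilbert's syndrome.
- **That the lost dose measures the problem.** A patient held permanently from Cycle 2 would miss 12 of the 14 planned olaratumab infusions and all six doxorubicin doses. Any cycle-start criterion that is never met gives the same count. The denominators are also maxima, because treatment can end earlier at resection or progression.
- **That every later cycle start carries the same risk.** A first hold late in treatment would require values below ULN at the earlier checks and then a rise. Holding for a new rise is a proper use of a hepatic criterion.

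**Conclusion.** The inconsistency is real, and the rule is wrong as written, at low severity. A Gilbert's patient with stable total bilirubin at or above ULN and under 3 mg/dL is eligible, receives the lead-in, and cannot start the combination without a deviation. A Gilbert's patient below ULN at the check can proceed.

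The conclusion rests on two assumptions: that the laboratory's ULN is below 3 mg/dL, and that the patient's bilirubin is unchanged when Cycle 2 is due. Its size is one patient's access to the combination for each patient affected, and that number may be zero. No effect on the primary biomarker analysis or on other trial-level results is claimed.

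**What to change.** Make the two limits agree, in the direction that the clinical team confirms.

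- **If doxorubicin is acceptable at that level:** add to the bilirubin item in Section 7.2.3.1 the same Gilbert's allowance as in criterion 9 (total bilirubin under 3 mg/dL). State any dose reduction that the package insert requires. Use "Direct bilirubin", already in the Attachment 2 chemistry panel, to confirm that any elevation is unconjugated.
- **If it is not acceptable:** delete the Gilbert's exception from criterion 9, so that patients who could not go on to the combination are not enrolled for the lead-in.

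The cost is one clinical confirmation and a one-line protocol amendment, plus the dose statement if the package insert calls for one. No new test is needed, and the sample size, primary analysis and SAP stay as they are.

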6.2. Summary of Study Design

Study JGDM is an open-label, single-arm, multicenter, multicountry Phase 1b study to enumerate whole blood CTCs and to characterize PDGFR α and PDGFR β and canonical ligands (*PDGF-A, B, C* and *D*) expression changes pre- and post-olaratumab monotherapy in tumor tissue in patients with potentially resectable STS.

Patients are to be treated with 20 mg/kg of olaratumab on Day 1 and Day 8 of Cycle 1, followed by up to 6 cycles (Cycle 2 – Cycle 7) of combination therapy with olaratumab plus doxorubicin. For Cycle 2, olaratumab is to be dosed at 20 mg/kg on Day 1 and Day 8 and doxorubicin is to be dosed at 75 mg/m² on Day 1. For Cycle 3 – Cycle 7, olaratumab is to be dosed at 15 mg/kg on Day 1 and Day 8 and doxorubicin is to be dosed at 75 mg/m² on Day 1. Each cycle of treatment is defined as an interval of 21 days. Approximately 35 patients are to be enrolled.

Starting with the first cycle of combination therapy (Cycle 2), the use of dexrazoxane (in a 10:1 ratio vs. doxorubicin dose) to mitigate cardiotoxicity during treatment with doxorubicin is allowed at the investigator's discretion and is recommended for all patients receiving 5 or more cycles of doxorubicin.

[figure not shown]
Tissue biopsies are required pre- and posttreatment with olaratumab monotherapy. The pretreatment tissue biopsy is to be performed within the screening period. The posttreatment tissue biopsy is to be performed after completion of the lead-in cycle of olaratumab monotherapy and prior to the initiation of combination therapy in Cycle 2. An optional third tissue biopsy (or tissue from a posttherapy surgical resection specimen) may be performed at the end of the patient's study treatment. If clinically feasible, the tissue biopsies should be taken from the same primary tumor lesion. If the patient has an additional surgical resection, tissue from this procedure is requested. Refer to Section 8.2.3.2 for details on tissue biopsies.

Whole blood samples for CTC analyses are to be collected predose at Cycle 1 Day 1 (C1D1), at Cycle 1 Day 8 (C1D8), at Cycle 2 Day 1 (C2D1), at Cycle 2 Day 8 (C2D8), at Cycle 3 Day 1 (C3D1), and at the end of the patient's study treatment or at the time of surgical resection. Refer to Section 8.2.3.1 for details on blood samples.

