Any patient who requires a dose reduction will continue to receive the reduced dose for the remainder of the study. Any patient who has had 2 dose reductions and who experiences a toxicity that would cause a third dose reduction must be discontinued from study drug.

In the event of an alteration in olaratumab dose due to an olaratumab-related toxicity, doxorubicin need not be altered, and the planned doxorubicin schedule should be maintained.

Similarly, olaratumab therapy need not be altered for doxorubicin-related toxicity. An alteration in doxorubicin dose will always necessitate a corresponding change to dexrazoxane, if administered, in order to maintain a dosage ratio of 10:1 (dexrazoxane:doxorubicin).

Discontinuations:

In general, discontinuation of olaratumab will not necessitate discontinuation of doxorubicin. In the event of discontinuation of olaratumab therapy due to an olaratumab-related toxicity or Grade 3 or 4 IRR, doxorubicin need not be altered, and the planned doxorubicin schedule may be maintained at the discretion of the investigator. Discontinuation of doxorubicin will necessitate discontinuation of olaratumab.

Any changes in treatments being added to or removed from patient care will be recorded on the eCRF.

The following information (in this section and the following subsections) pertains to dose modifications and delays for and management of AEs of concern, which may or may not be associated with olaratumab therapy, including the following:

- IRR (see Section 7.2.3.1.1.1)
- Hematologic toxicity (see Section 7.2.3.1.1.2)
- Nonhematologic toxicity (see Section 7.2.3.1.1.3)

The following information (in this section and the following subsections) pertains to dose modifications and delays for and management of AEs of concern, which may or may not be associated with doxorubicin therapy, including the following:

- Hematologic toxicity (see Section 7.2.3.1.2.1)
- Cardiovascular toxicity (see Section 7.2.3.1.2.2)
- Hepatic impairment (see Section 7.2.3.1.2.3)
- Nonhematologic toxicity (Section 7.2.3.1.2.4)

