A Grade 3 or 4 IRR will require immediate treatment, including the use of epinephrine, bronchodilators, and/or glucocorticoids for symptomatic bronchospasm, IV fluids and/or pressors for hypotension, and immediate and permanent discontinuation of olaratumab with appropriate supportive care.

If a patient experiences an IRR to olaratumab, all attempts should be made to obtain an anti-olaratumab antibody blood sample as close to the onset of the event as possible, at the resolution of the event, and 30 days (± 3 days) following the event. In addition, these same samples may be assessed for levels of olaratumab and for pharmacodynamic markers to provide information on the nature of the IRR. The procedure for sample collection and handling is described in a separate procedural manual.

Section 7.1.3 provides information on doxorubicin and IRRs.

7.2.3.1.1.2. Hematologic Toxicity

Table JGDM.2 summarizes the olaratumab dose modifications required in case of hematological toxicities.

Table JGDM.2. General Guidelines for Olaratumab Dose Modification Due to Hematologic Toxicity Deemed Related to Olaratumab

Toxicity	Required Dose Modification
Neutropenia	
ANC Grade 1-3	No dose modification required.
ANC <500 cells/ μ L (Grade ≥ 4)	No treatment administered; treatment cycle delayed.
At retreatment:	
If Grade ≥ 3 neutropenic fever/infection has occurred	Withhold dose until ANC is 1000 cells/ μ L or higher; reduce dose to 12 mg/kg (15 mg/kg if toxicity occurs during Cycle 1 or Cycle 2).
If Grade 4 neutropenia lasting longer than 1 week has occurred	Withhold dose until ANC is 1000 cells/ μ L or higher; reduce dose to 12 mg/kg (15 mg/kg if toxicity occurs during Cycle 1 or Cycle 2).
Grade 4 ANC without fever/infection	Retreatment with olaratumab at full dose at investigator's discretion with recommended use of prophylactic G-CSFs.
Second incidence of either: 1) Grade ≥ 3 neutropenic fever/infection 2) Grade 4 neutropenia lasting longer than 1 week	Second dose reduction to 10 mg/kg.
Thrombocytopenia	
Platelets <75,000 cells/ μ L (Grade 1)	No treatment administered; treatment delayed until resolved to $\geq 100,000$ cells/ μ L.
Anemia	
Hemoglobin <9 gm/dL (Grade 2)	No treatment administered; treatment delayed until resolved to \leq Grade 1.

Abbreviations: ANC = absolute neutrophil count; G-CSF = granulocyte colony-stimulating factor.

7.2.3.1.1.3. Nonhematologic Toxicity

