Specific guidelines for dose adjustments in patients who experience olaratumab IRRs may be found in Section 7.2.3.1.1.1.

Table JGDM.3 provides general guidelines for dose modification for other nonhematologic toxicities related to olaratumab. If more than 2 toxicity-related olaratumab dose reductions are required, treatment with this agent will be permanently discontinued.

Table JGDM.3. General Guidelines for Olaratumab Dose Modification Due to Nonhematologic Toxicity Deemed Related to Olaratumab

Reaction Grade	Required Dose Modification
Grade 1	No dose modification is required.
Grade 2	At the investigator's discretion, the patient may continue to receive olaratumab per protocol, provided that the event does not pose a serious health risk or is easily treated.
Grade 3	For a Grade 3 toxicity not adequately controlled with appropriate supportive care, the dose must be withheld until toxicity is Grade ≤ 1 or has returned to pretreatment baseline; then treatment may resume at a reduced dose of 12 mg/kg (15 mg/kg if the toxicity occurs during Cycle 1 or Cycle 2). If toxicity recurs after therapy resumes, a second dose reduction (to 10 mg/kg) is permitted.
Grade 4	The dose must be withheld until dose toxicity is \leq Grade 1 or has returned to baseline. Permanent discontinuation should be considered for any patient experiencing Grade 4 nonhematological toxicity assessed as related to olaratumab. However, if resumption of dosing is deemed appropriate by the investigator, treatment may resume only after consultation with the Lilly study physician, with the dose reduced to 10 mg/kg (15 mg/kg if the toxicity occurs during Cycle 1 or Cycle 2). If Grade 4 toxicity recurs after therapy resumes, olaratumab treatment will be discontinued.

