7.2.3.1.2. Doxorubicin

7.2.3.1.2.1. Hematologic Toxicity

Doxorubicin will not be administered after the initial dose if the patient's ANC is <1000 cells/ μL or if the platelet count is $<100,000$ cells/ μL . When necessary, the next treatment cycle should be delayed until the ANC is ≥ 1000 cells/ μL and the platelet count is $\geq 100,000$ cells/ μL and nonhematologic toxicities have resolved. For patients who experience \geq Grade 3 neutropenic fever or infection or Grade 4 neutropenia without fever lasting more than 1 week, doxorubicin should be reduced to 75% of the starting dose (that is, to approximately 60 mg/ m^2). If a patient experiences a second incidence of neutropenic fever/infection or has another episode of Grade 4 neutropenia lasting >1 week, then a second dose reduction to 45 mg/ m^2 will be necessary. Therapeutic and prophylactic use of pegfilgrastim (Neulasta[®]) or other G-CSFs will be allowed per current American Society of Clinical Oncology (ASCO; Smith et al. 2006) and National Comprehensive Cancer Network (NCCN) guidelines (NCCN 2014). For patients with Grade 4 ANC without fever/infection lasting less than 1 week, retreatment will be allowed at the investigator's discretion with the full dose of doxorubicin (75 mg/ m^2) with recommended use of

G-CSFs per current ASCO guidelines (Smith et al. 2006). See [Table JGDM.4](#) for doxorubicin dose modification for neutropenia.

Table JGDM.4. General Guidelines for Doxorubicin Dose Modification Due to Neutropenia

Toxicity	Required Dose Modification
ANC <1000 cells/ μ L	No doxorubicin administered; treatment cycle delayed.
At pretreatment:	
If Grade ≥ 3 neutropenic fever/infection has occurred	Approximately 60 mg/m ² doxorubicin.
If Grade 4 neutropenia lasting longer than 1 week has occurred	Approximately 60 mg/m ² doxorubicin.
Grade 4 ANC without fever/infection	Retreatment with doxorubicin at full dose at investigator's discretion with recommended use of prophylactic G-CSFs.
Second incidence of either:	
1) Grade ≥ 3 neutropenic fever/infection	Second dose reduction to 45 mg/m ² .
2) Grade 4 neutropenia lasting longer than 1 week	

Abbreviations: ANC = absolute neutrophil count; G-CSF = granulocyte colony-stimulating factor.

7.2.3.1.2.2. Cardiovascular Toxicity

Cardiotoxicity is a recognized risk of doxorubicin that increases with higher cumulative drug exposure. Cardiac monitoring is conducted by a combination of monitoring of clinical parameters, ECG, and ECHO/MUGA scans.

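### Protocol Section 7.2.3.1 keeps a reduced dose for the rest of the study, but the full-dose retreatment rules do not exclude patients already reduced, and no text says which prevails

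*Protocol*

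**What the plan says.** Section 7.2.3.1 (Dose Modifications) gives two general rules. The first is "Any patient who requires a dose reduction will continue to receive the reduced dose for the remainder of the study". The second limits the number of steps: "Any patient who has had 2 dose reductions and who experiences a toxicity that would cause a third dose reduction must be discontinued from study" (meaning study drug).

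The drug-specific subsections then set doses by type of event.

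- **Doxorubicin (Section 7.2.3.1.2.1, Table JGDM.4).** A first neutropenic fever or infection of Grade 3 or higher, or a first Grade 4 neutropenia lasting over a week, leads to 75% of the starting dose, glossed as approximately 60 mg/m². A second such event leads to 45 mg/m². After Grade 4 ANC without fever or infection lasting less than a week, retreatment is allowed at the investigator's "discretion with the full dose of doxorubicin", with 75 mg/m² in parentheses. Table JGDM.4 repeats the full-dose wording.
- **Olaratumab, hematologic (Table JGDM.2).** The first neutropenic event of the same kinds leads to "reduce dose to 12 mg/kg (15 mg/kg if toxicity occurs during Cycle 1 or Cycle 2", and the second to 10 mg/kg. A parallel row for Grade 4 ANC without fever or infection allows full dose at the investigator's discretion.
- **Olaratumab, nonhematologic (Table JGDM.3).** For an inadequately controlled Grade 3 event the dose is withheld, "then treatment may resume at a reduced dose of 12 mg/kg" (15 mg/kg in Cycles 1 and 2). After a Grade 4 event, dosing may resume only after consultation with the sponsor's physician, "with the dose reduced to 10 mg/kg (15 mg/kg if the toxicity occurs during Cycle 1 or Cycle 2".

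The planned olaratumab doses come from Section 6.2. Cycle 1 uses 20 mg/kg, "For Cycle 2, olaratumab is to be dosed at 20 mg/kg on Day 1 and Day 8", and for Cycles 3 to 7 "olaratumab is to be dosed at 15 mg/kg on Day 1 and Day 8".

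**The concern.** The general rule depends on the dose the patient is already on. The event rows do not: each names full dose or a fixed mg/kg or mg/m² figure, whatever the current dose. The two fit together for a first toxicity. For a second toxicity of a different kind they can point to different doses.

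The patients concerned have already had a toxicity that led to a reduction and are now having another. Sites could handle the same event differently and each cite protocol text for it. For doxorubicin the difference carries over to dexrazoxane, which Section 7.2.3.1 ties to the doxorubicin dose at 10:1. Two counts also depend on what is called a reduction: the one that triggers discontinuation under the third-reduction rule, and the SAP's number of dose level reductions (Section 5.3.4), which is summed as reported in the eCRF.

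**Working it through.** There is no statistical figure to reproduce. The check sets the general rule beside each row for a patient already below the planned dose. The term full dose is defined for doxorubicin (75 mg/m²) but not for olaratumab. For olaratumab it is read here as the planned dose of the cycle, which is an assumption.

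| Current dose and how reached | Next event | Section 7.2.3.1 | Drug-specific text | Ratio |
|---|---|---|---|---|
| Doxorubicin, approximately 60 mg/m², after a first qualifying neutropenic event | Grade 4 ANC, no fever or infection, under 1 week | keep 60 | 75 allowed | 75/60 = 1.25 |
| The same, with the reduction taken as 0.75 × 75 = 56.25 mg/m² | same | keep 56.25 | 75 allowed | 75/56.25 = 1.33 |
| Doxorubicin 45 mg/m², after a second qualifying event | same | keep 45 | 75 allowed | 75/45 = 1.67 |
| Olaratumab 12 mg/kg, Cycles 3–7 | Grade 4 ANC, no fever or infection | keep 12 | full dose (15) allowed | 15/12 = 1.25 |
| Olaratumab 10 mg/kg, Cycles 3–7, after a Grade 4 nonhematologic event | same | keep 10 | full dose (15) allowed | 15/10 = 1.50 |
| Olaratumab 15 mg/kg, reduced in Cycles 1–2 | same, still in Cycles 1–2 | keep 15 | full dose (20) allowed | 20/15 = 1.33 |
| Olaratumab 10 mg/kg, Cycles 3–7, after a Grade 4 nonhematologic event | first uncontrolled Grade 3 nonhematologic event, or first qualifying neutropenic event | keep 10 | reduce to 12 | 12/10 = 1.20 |

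The two doxorubicin figures come from one sentence of Section 7.2.3.1.2.1, where 75% of the starting dose and approximately 60 mg/m² do not quite agree (60/75 = 80%). Hence the range of +25% to +33%.

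Taking every pair of olaratumab events, with each event in Cycles 1–2 or in Cycles 3–7, eight pairs give a table dose above an already reduced dose. Six come from the full-dose row. The other two are the 10-to-12 cases in the last line of the table.

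The third-reduction rule does not settle these pairs, since each involves only one earlier reduction. It does not clearly settle the doxorubicin 45 mg/m² line either, because the full-dose row is not a reduction.

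Many sequences do not conflict. A patient at 12 mg/kg who has a first event of the other kind stays at 12. A reduction to 15 mg/kg in Cycles 1–2 equals the planned dose from Cycle 3. The doxorubicin Grade 4 nonhematologic rule (Section 7.2.3.1.2.4) allows 60 mg/m² or less, so it does not force a rise.

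**Effect on the primary analysis.** Cycle 1 has two olaratumab doses, on Days 1 and 8. A reduced dose can be given on Day 8 at the earliest, so a rise from it could come no sooner than Cycle 2 Day 1. The second biopsy and the Cycle 2 Day 1 blood draw both precede that dose, and doxorubicin starts only in Cycle 2. The pre/post-monotherapy comparison is untouched.

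**The case against.** The best reply is that Section 7.2.3.1 already supplies the rule. The drug-specific sections are its subsections and are introduced as part of the same body of guidance, and the tables are titled as general guidelines. On that reading a row says whether this event triggers a reduction, and the general rule says that a past reduction stays. This is reasonable, but the protocol does not say it. The table column is headed as required modification, and a reader could equally take the specific row as an exception to the general one. With 75 mg/m² printed, full dose for doxorubicin cannot readily be read as the current reduced dose.

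A reader might infer that the two texts give opposite instructions, so that a site must break one to follow the other. The documents do not support that. The full-dose rules are permissions, and a site that keeps the reduced dose breaches nothing.

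A reader might also infer that Tables JGDM.2 and JGDM.3 order an increase from 10 to 12 mg/kg. They do not, because both rows speak of reducing, and 12 is not a reduction from 10. The row simply has no meaning for that patient. The sequence is also remote: it needs an olaratumab-related Grade 4 nonhematologic event for which permanent discontinuation should be considered, sponsor consultation before resuming, and then a second qualifying event.

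The effect on the SAP is small. The count of reductions is a descriptive safety summary, and Section 8.1.2 already requires sites to report the circumstances of any reduction.

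**Conclusion.** The point holds in limited form. For a patient already reduced who then has a short afebrile Grade 4 neutropenia, one part of the protocol permits a return to full dose that another part forbids, and precedence is not stated. For doxorubicin at the first reduced level the gap is +25%, or +33% if 56.25 mg/m² is used. The olaratumab full-dose row has the same defect, with a size that depends on what full dose means. The olaratumab 10-to-12 mg/kg case (+20%) is secondary: a row that cannot be applied as worded, not an order to escalate.

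The documents give no frequency for such sequences. Each affected patient would be 1/35 = 2.9% of the planned enrollment, which is a unit and not an estimate. Since a second qualifying toxicity after a reduction is needed, few patients are likely to be affected. Sample size and the primary biomarker analysis are not affected. This is a clarification worth making for consistent handling of patients with repeat toxicity; the trial's conclusions do not depend on it.

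**What to change.** The sponsor's clinical team should reconcile the Dose Modifications text of Section 7.2.3.1 with Sections 7.2.3.1.1.2, 7.2.3.1.1.3 and 7.2.3.1.2.1 and Tables JGDM.2 to JGDM.4. Each full-dose row and each fixed-dose row should state how it applies to a patient already below the starting dose. The term full dose should be defined for olaratumab, and one sentence should say which text takes precedence. The eCRF instructions, and through them the SAP count of dose level reductions, should then follow the reconciled rule. Which rule should prevail, and at what dose, is a clinical decision on which nothing is proposed here.

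The cost is protocol wording in one section and three tables plus a line of eCRF guidance. No extra patients, visits or data are needed.
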